3.1.1 Definition of Treatment Cycle and Duration

Ramucirumab and pembrolizumab will be administered on day 1 of each cycle. One cycle is defined as 21 days.

3.1.2 Timing of Dose Administration

Trial treatment should be administered on Day 1 of each cycle after all procedures/assessments have been completed as detailed on the Trial Flow Chart (Section 6.3). Trial treatment may be administered up to 3 days before or after the scheduled Day 1 of each cycle due to administrative reasons.

All trial treatments will be administered on an outpatient basis. Ramucirumab will be administered first followed by pembrolizumab.

Ramucirumab 10 mg/kg will be administered as an IV infusion every 3 weeks. Administer initial infusion over 60 minutes; if tolerated, may administer subsequent infusions over 30 minutes starting with cycle 2. Given the variability of infusion pumps from site to site, a window of -5 minutes and +10 minutes is permitted (i.e., infusion time is 30 minutes: -5 min/+10 min).

Pembrolizumab 200 mg will be administered as a 30 minute IV infusion every 3 weeks. Sites should make every effort to target infusion timing to be as close to 30 minutes as possible. However, given the variability of infusion pumps from site to site, a window of -5 minutes and +10 minutes is permitted (i.e., infusion time is 30 minutes: -5 min/+10 min).

The Pharmacy Manual contains specific instructions for the preparation of the pembrolizumab infusion fluid and administration of infusion solution.

3.1.3 Treatment Phase

Treatment will be continued for up to 35 cycles until confirmed progression of disease is demonstrated by CT scan, unacceptable toxicities occur in individual subjects, or consent is withdrawn.

3.1.4 End of Treatment Visit

Patients that discontinue from treatment will undergo an end of treatment visit, regardless of the reason of discontinuation, 30 (+/- 14) days after the last dose of study medication.

This study to be conducted at The Ohio State University Wexner Medical Center. If the protocol meets criteria to proceed with enrollment after initial futility analysis, we will consider expansion to include additional sites.

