1.4 Clinical Safety

Pembrolizumab and ramucirumab are both approved by the Food and Drug Administration (FDA) for commercial use in NSCLC but have not been approved in combination. Measures will be taken to ensure the safety of the patients participating in this trial including the use of stringent inclusion and exclusion criteria and close monitoring. Toxicity grading will be performed in accordance with NCI CTCAE, Version 5.0. If more than one different type of toxicity occurs concurrently, the most severe grade will determine the modification.

If toxicities are encountered, adjustments will be made to the study treatment as detailed in the sections below. All AEs and SAEs will be recorded during the trial and for up to 30 days after the last dose of study treatment or until the initiation of another anti-cancer therapy, whichever occurs first.

1.5 Phase II Single Arm Trial of Ramucirumab and Pembrolizumab in EGFR mutant Non-Small Cell Lung Cancer

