6.1 Study Assessments

6.1.1 Efficacy Assessments

Primary Endpoint: The response rate of R+P will be evaluated using RECIST 1.1 as well as iRECIST. Disease status will be measured by CT scan at baseline and then once every two cycles and as clinically indicated. Radiographic response per RECIST v.1.1 and iRECIST criteria (Appendices 1 and 2) will be determined by comparison to the tumor measurement obtained at baseline. Tumor progression will be determined by comparison to the smallest tumor measurement at either baseline or after initiation of therapy. The baseline disease assessment must be recorded and measured within 28 days prior to treatment start. During the treatment period, disease assessments will be performed every 6 weeks, i.e. once every two cycles, and as clinically indicated.

Secondary Endpoints: Safety and tolerability will be assessed with adverse event (AE) assessments at each study visit. CTCAE v5.0 will be used for adverse event grading. Attributions of causality will be assessed by the primary treating physician. Clinical benefit rate (stable disease + responses) will be assessed using the same criteria as response rate and on the same schedule. Survival will be measured from the date of study registration to the date of event (i.e., death or progressive disease) or the date of last follow-up if no event has occurred at their last evaluation.

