6.2 Data Safety and Monitoring Plan

The data and safety monitoring plan will involve the continuous evaluation of safety, data quality and data timeliness. Investigators will conduct continuous review of data and patient safety at their regular disease group meetings (at least monthly) and the discussion will be documented in the minutes. The PI of the trial will review toxicities and responses of the trial where applicable at these disease group meetings and determine if the risk/benefit ratio of the trial changes. Frequency and severity of adverse events will be reviewed by the PI and compared to what is known about the agent/device from other sources; including published literature, scientific meetings and discussions with the investigators, to determine if the trial should be terminated before completion. Serious adverse events and responses will also be reviewed by the OSUCCC Data and Safety Monitoring Committee (DSMC). The PI will also submit a progress report (biannually for Phase II and quarterly for Phase I) that will be reviewed by the committee per the DSMC plan. All reportable Serious Adverse Events (SAE) will also be reported to the IRB of record as per the policies of the IRB.

Throughout the treatment period until one month after the last dose of study medication, patients will be assessed for all adverse events. National Cancer Institute Common Terminology Criteria for Adverse Events (CTCAE v 5.0) will be used for grading. If necessary, the patient may be withdrawn from the study treatment.

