6.3 Schedule of Study Events

The Schedule of Study Events is shown in Table 4**Table 4**.

PROTOCOL NUMBER: OSU-19132

Table 4. Schedule of Study Events

Assessments	Screening/ Baseline			Cycle 1*	Cycle 1	Cycle 2	Cycle 2	Cycle 3 +	End of Treatment
Visit window [days]	Within 28 days	Within 10 days	Within 7 days	Day 1	Day 8	Day 1	Day 8	Day 1	30 days
						+/- 3 days		+/- 3 days	± 14 days
Informed consent ¹	X								
Inclusion and exclusion criteria		X							
Demographics		X							
Medical History ²		X							X
Pregnancy test (if applicable) ³		X						X	
Vital signs and weight ⁵		X		X	X	X	X	X	X
Physical examination and ECOG			X	X	X	X	X	X	X
Urine analysis ⁶		X		X	X	X	X	X	X
Hematology ⁷		X		X				X	X
Coagulation studies ⁸		X						X ⁷	
Complete Serum chemistry ⁹		X		X	X	X	X	X	X
TSH ¹⁰		X						X ⁹	
Peripheral blood correlative studies ¹¹				X				X ¹¹	X
Tumor biopsy ¹¹	X								X
Assessment of disease status ¹²	X							X	X
Ramucirumab dosing				X		X		X	
Pembrolizumab dosing				X		X		X	
Adverse event assessment				X		X		X	X
Concomitant Medication		X		X		X		X	X

Study Assessment Footnotes

PROTOCOL NUMBER: OSU-19132

* Each treatment cycle is 21 days

¹ Prior to the first study-specific assessments

² Medical history includes baseline symptoms as well as a detailed history of prior cancer therapies including start and stop dates, disease progression during or after therapy, as well as discontinuations due to intolerance or any other serious illness.

³ Applicable for women of childbearing potential. Serum β -HCG test within 14 days before the first dose of study drug.

⁴ Urine pregnancy test on day 1 of cycle 1 to confirm pregnancy status prior to treatment. Repeat urine pregnancy testing for women of childbearing potential every 9 weeks or if pregnancy is suspected. Positive urine pregnancy testing will require confirmation with serum pregnancy testing.

⁵ Vital signs: Weight, blood pressure, pulse and temperature

⁶ Urine analysis will include appearance, color, glucose, hemoglobin, ketones, pH, and protein. Microscopy will only be performed if clinically indicated. Urine dipstick protein $> 1+$ will require 24 hour urine collection for urine protein assessment. 24 urine collection will include measurement of both protein and creatinine.

⁷ Hematology: Complete blood count including differential is required. WBC differential may be automated or manual as per institutional standards.

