6.3.6 End of Treatment and Follow-up Tumor Imaging

Patients who discontinue therapy for any reason must have an end of treatment (EOT) visit completed 30 days (\pm 14 days) after the last application of study drug.

At the EOT visit, the patients will undergo the following assessments:

Physical examination and vital signs	
• Body weight• Blood pressure, pulse, temperature• Physical examination
Urine analysis	Urine bilirubin, glucose, hemoglobin, ketones, pH, protein
Hematology	Hemoglobin, hematocrit, mean corpuscular volume, mean corpuscular hemoglobin, mean corpuscular hemoglobin concentration, white blood cell (WBC) count, WBC differential, red blood cell count, lymphocytes, monocytes, neutrophils, band neutrophils, eosinophils, basophils, platelets. WBC differential may be automated or manual as per institutional standards.
Complete serum chemistry	Sodium, potassium, chloride, bicarbonate, BUN, creatinine, glucose, calcium, phosphate, magnesium, ALT, AST, alkaline phosphatase, total bilirubin, total protein, albumin
Assessment of disease status	CT scan (if not performed within the last 28 days)
Adverse events and concomitant medication	Assessed on an ongoing basis

PROTOCOL NUMBER: OSU-19132

In participants who discontinue study treatment, tumor imaging should be performed at the time of treatment discontinuation (± 4 week window). If previous imaging was obtained within 4 weeks prior to the date of discontinuation, then imaging at treatment discontinuation is not mandatory. In participants who discontinue study treatment due to documented disease progression and the Investigator elects not to implement iRECIST, this is the final required tumor imaging.

In participants who discontinue study treatment without documented disease progression, every effort should be made to continue monitoring their disease status by tumor imaging using the same imaging schedule used while on treatment (every 12 weeks in Year 1 or every 24 weeks after Year 1) to monitor disease status until the start of a new anticancer treatment, disease progression, pregnancy, death, withdrawal of consent, or the end of the study, whichever occurs first.

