6.3.7 Post-treatment follow-up

Patient status will continue to be evaluated post-study. Patients will be contacted via telephone every 3 months for the first year after study completion. Beyond 1 year post-treatment, patients will be contacted every 6 months to obtain information for post-study survival data. Patients will be asked to supply the name and addresses of two contact people who the site may contact to assist with phone follow-up. Post-study survival data may alternatively be obtained during patient visits to site or source documents from other medical visits.

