13.5 Reporting to the Drug Provider (Merck)

An adverse event is defined as any untoward medical occurrence in a patient or clinical investigation participant administered a pharmaceutical product and which does not necessarily have to have a causal relationship with this treatment. An adverse event can therefore be any unfavorable and unintended sign (including an abnormal laboratory finding, for example), symptom, or disease temporally associated with the use of a medicinal product or protocol-specified procedure, whether or not considered related to the medicinal product or protocol-specified procedure. Any worsening (i.e., any clinically significant adverse change in frequency and/or intensity) of a preexisting condition that is temporally associated with the use of the Merck's product, is also an adverse event.

Changes resulting from normal growth and development that do not vary significantly in frequency or severity from expected levels are not to be considered adverse events. Examples of this may include, but are not limited to, teething, typical crying in infants and children and onset of menses or menopause occurring at a physiologically appropriate time.

Merck product includes any pharmaceutical product, biological product, device, diagnostic agent or protocol-specified procedure, whether investigational (including placebo or active comparator medication) or marketed, manufactured by, licensed by, provided by or distributed by Merck for human use.

Adverse events may occur during the course of the use of Merck product in clinical trials, or as prescribed in clinical practice, from overdose (whether accidental or intentional), from abuse and from withdrawal.

All AEs, SAEs and other reportable safety events that occur after the consent form is signed but before treatment allocation/randomization must be reported by the investigator if the participant is receiving placebo run-in or other run-in treatment, if the event cause the participant to be excluded from the study, or is the result of a protocol-specified intervention, including but not limited to washout or discontinuation of usual therapy, diet, or a procedure.

- All AEs from the time of treatment allocation/randomization through 30 days following cessation of study treatment must be reported by the investigator.

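### The last scheduled adverse event assessment may fall on day 16 after the last dose, so the schedule does not guarantee the 30-day adverse event window the protocol states

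*Combined protocol and SAP*

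**What the plan says.** **The window.** Section 1.4 states: "All AEs and SAEs will be recorded during the trial and for up to 30 days after the last dose of study treatment". It closes the window earlier if another anti-cancer therapy begins, and Section 7.2 repeats both parts. Section 6.2 puts it this way: "Throughout the treatment period until one month after the last dose of study medication, patients will be assessed for all adverse events". Section 13.5 adds a duty: "All AEs from the time of treatment allocation/randomization through 30 days following cessation of study treatment must be reported by the investigator". Neither Section 6.2 nor that sentence of Section 13.5 carries the new-therapy exception.

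**The last AE visit.** Section 3.1.4 says that patients who stop treatment "will undergo an end of treatment visit, regardless of the reason of discontinuation, 30 (+/- 14) days after the last dose of study medication". Section 6.3.6 confirms that they "must have an end of treatment (EOT) visit completed 30 days" after the last dose, with the same 14-day tolerance, as does the last column of Table 4.

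**After that visit.** Section 6.3.7 plans calls: "Patients will be contacted via telephone every 3 months for the first year after study completion". The data it names are survival data; it does not mention AEs.

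**AE assessments during treatment.** Section 6.1.1 says: "Safety and tolerability will be assessed with adverse event (AE) assessments at each study visit". In Table 4 the row "Adverse event assessment" is marked at Day 1 of Cycles 1, 2 and 3 onward and at end of treatment. It is blank at Day 8 of Cycles 1 and 2.

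**The concern.** Safety and tolerability are secondary endpoints. Section 9.4.2 summarises them by each patient's maximum grade per toxicity and by the incidence of grade 3 or higher events. Both summaries depend on all patients being asked about AEs over the same period. If one patient's final assessment is on day 16 and another's is on day 35, the first has been asked about only part of the stated window. Capture may then vary with visit timing and not only with toxicity. Sections 7.1 and 7.2 say that the full safety profile of the combination is not yet known, so even capture matters here.

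The blank Day 8 cells raise a smaller question: whether sites should follow the text or the table.

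**Working it through.** The plan gives no figure of its own on this point. The check sets the passages side by side and does the arithmetic on days.

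**1. Permitted days for the end of treatment visit.** Sections 3.1.4 and 6.3.6 and Table 4 give 30 ± 14 days. Earliest: 30 − 14 = day 16. Latest: 30 + 14 = day 44.

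**2. Days of the window after the last scheduled AE assessment.** For a visit on day D, the gap is max(0, 30 − D).

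| Visit day D | Gap (days) | Share of 30 days |
|---|---|---|
| 16 | 14 | 14/30 = 47% |
| 23 | 7 | 7/30 = 23% |
| 30 to 44 | 0 | 0% |

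If new anti-cancer therapy starts on day T and Sections 1.4 and 7.2 apply, the gap becomes max(0, min(30, T) − D). It is zero whenever T is no later than D.

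**3. Is there another scheduled AE contact in the gap?**
- Section 6.3.7: the calls are three-monthly, and AEs are not mentioned.
- Section 6.3.6: imaging continues for patients who stop without progression. This may bring some of them in sooner, but it is not an AE assessment.
- Section 6.6: patients withdrawn for a medical reason stay under supervision until existing AEs resolve or return to baseline. Nothing is scheduled to find new ones.
- Section 4.5: toxicity follow-up continues after 35 cycles and is optional for others. No timetable is given.

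None of these guarantees an AE contact between day 16 and day 30.

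**4. Day 8 visits.** The Table 4 columns line up. The ramucirumab row is marked at Day 1 of Cycles 1, 2 and 3 onward only. Vital signs and examination are marked at every on-treatment visit, including both Day 8 visits. The AE and concomitant medication rows are blank at both Day 8 visits. The synopsis list for Cycle 1 Day 8 also omits AEs, while its Cycle 1 Day 1, later-cycle and final-visit lists include them. An extraction fault is therefore unlikely.

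**5. What one missed patient does to an incidence.** If a patient's only grade 3 or higher event is missed, the incidence shifts by 1/34 = 2.9 percentage points in the full trial, or 1/13 = 7.7 points if the trial stops after stage 1.

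**6. Serious events.** Sections 1.4, 7.2 and 13.2 give 30 days. Sections 13.5 and 13.5.3 give 90 days, or 30 if new anticancer therapy starts, whichever is earlier. Against 90 days, the time after the last scheduled AE assessment is 90 − 44 = 46 days to 90 − 16 = 74 days.

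**The case against.** The strongest reply is that AE collection does not stop at the end of treatment visit. Section 13.5 obliges the investigator to report all AEs through day 30, and Section 6.2 says assessment runs for a month. Section 6.3.6 also describes AE assessment as continuing, in the end of treatment list itself. This stands, and it limits the point to a gap in scheduled contact.

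Some stronger readings are tempting but not supported:
- **Events after an early visit go uncounted.** No passage ends collection there. They may be missed, because nothing scheduled prompts the question.
- **The continuing-assessment wording applies only on treatment.** It appears in Section 6.3.2, but Section 6.3.6 repeats it. Even so, it schedules no later contact.
- **About half of patients would have a gap.** The documents say nothing about how visit days are distributed within the tolerance, and new therapy would close some gaps. Only the range of 0 to 14 days is supported.
- **The Day 8 blanks leave part of the window uncovered.** They do not, because the next Day 1 visit can ask about the interval. A percentage of visits without AE assessment would also depend on how many cycles are counted.

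It can also be said that Section 7.2.2 expects some immune events months after the last dose, which a day-30 call would not find. That is true. The call secures only the stated 30-day window; late serious events depend on settling the 30-day and 90-day conflict.

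**Conclusion.** The point holds as a gap between the stated AE window and the schedule meant to deliver it. The gap is 0 to 14 days per patient, at most 47% of the window. It is smaller or absent where new anti-cancer therapy starts before day 30 and the exception in Sections 1.4 and 7.2 applies. The 14-day maximum follows from the visit tolerance alone and needs no assumption. The number of patients affected and the number of events missed cannot be derived from the documents.

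The Day 8 omission is a contradiction between Section 6.1.1 and Table 4, with no demonstrated loss of safety data. The two windows for serious events are a further contradiction that must be resolved. None of this affects the primary endpoint, but it bears on a secondary endpoint in a trial of at most 34 patients and is cheap to correct.

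**What to change.** 1. In Table 4, mark AE assessment and concomitant medication at Day 8 of Cycles 1 and 2, and bring the synopsis Day 8 list into line.
2. In Sections 3.1.4 and 6.3.6, add that when the end of treatment visit is held before day 30 and no new anti-cancer therapy has started, a documented AE telephone check follows on or after day 30.
3. State once whether new anti-cancer therapy closes the AE window, and make Sections 1.4, 6.2, 7.2 and 13.5 agree.
4. Reconcile the serious-event windows in Sections 1.4, 7.2 and 13.2 with those in Sections 13.5 and 13.5.3, and say how events are to be sought up to whichever limit is kept.

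The cost is two marks in each of two table rows, some text edits, and one call for each patient seen early. No extra clinic visit or design change is needed.

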3.2 Study Duration

Patients will receive pembrolizumab and ramucirumab day 1 during each 21-day cycle. Patient may continue on study drugs until disease progression or for up to 35 cycles. Objective assessment of disease progression will be performed every six weeks.

IRB Protocol Number: 2019C0145
IRB Approval date: 06/10/2022
Version: 05/06/2022

PROTOCOL NUMBER: OSU-19132

[figure not shown]
The study enrolled first patient in Summer 2020 with respect to first patient in (FPI). With an expected accrual rate of 1 patients every 2months, and a total number of 34 patients planned (if trial proceeds to second stage), the anticipated enrollment period is 60 months with the last patient enrolled by Summer2025. The anticipated length of treatment period will be approximately 3-6 months, leading to the last patient off study treatment in November-December 2025. The primary endpoint analysis will be done after the last accrued patient has been followed for at least 6 weeks.

IRB Protocol Number: 2019C0145
IRB Approval date: 06/10/2022
Version: 05/06/2022

PROTOCOL NUMBER: OSU-19132

[figure not shown]

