4.1 Study Population and Sample Size

This trial will be open to non-small cell lung cancer (NSCLC) patients with sensitizing EGFR mutations who have received first or second line therapy with tyrosine kinase inhibitor (TKI). These are most commonly lung adenocarcinoma but there are no restrictions for histology.

Planned enrollment is up to 34 patients. There will be a 2 stage design with a planned interim analysis for futility planned after the initial 13 patients (stage 1) have been followed for at least 6 weeks.

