⁸ Coagulation studies will include PT/INR and PTT. These studies will be repeated every 3rd cycle or as needed (for patients on active anti-coagulation).

⁹ Complete Serum Chemistry includes: sodium, potassium, chloride, bicarbonate, BUN, creatinine, glucose, calcium, phosphate, magnesium, ALT, AST, alkaline phosphatase, total bilirubin, total protein, albumin.

¹⁰ TSH will be performed at baseline - free T3/free T4 to be checked if TSH is out of the normal range.

¹¹ Correlative studies (peripheral blood) will be drawn pre-treatment on cycle 1 day 1; cycle 3 day 1, and at final study visit. Tumor biopsy sample (archival) will be collected at study enrollment. Optional tumor biopsy at progression if clinically indicated.

¹² Disease status will be measured by CT scan every 6 weeks (+/- 7 days) for the first 6 months and then every 12 weeks and as clinically indicated. Baseline imaging within 28 days of study initiation.

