6.3.5 Tumor Imaging on Study

The first on-study imaging assessment should be performed at 6 weeks (42 days \pm 7 days) from the date of allocation. Subsequent tumor imaging should be performed every 6 weeks (42 days \pm 7 days) or more frequently if clinically indicated. After 6 months, participants who remain on treatment will have imaging performed every 12 weeks (84 days \pm 7 days). Imaging timing should follow calendar days and should not be adjusted for delays in cycle starts. Imaging should continue to be performed until disease progression is identified by the Investigator.

Objective response should be confirmed by a repeat imaging assessment. Tumor imaging to confirm PR or CR should be performed at least 4 weeks after the first indication of a response is observed. Participants will then return to regular scheduled imaging every 6 weeks, starting with the next scheduled imaging time point. Participants who receive additional imaging for confirmation do not need to undergo the next scheduled tumor imaging if it is less than 4 weeks later; tumor imaging may resume at the subsequent scheduled imaging time point.

PROTOCOL NUMBER: OSU-19132

Per iRECIST (Appendix 2), disease progression should be confirmed by the site 4 to 8 weeks after first radiologic evidence of PD in clinically stable participants as defined by Appendix 2 (Note- if patient is receiving clinical benefit, oligoprogressive CNS disease that can be controlled with local therapy such as stereotactic radiation, may continue on treatment beyond progression with PI approval. Ramucirumab should be held for 2 weeks prior to radiation. Patient can have radiation for CNS oligoprogression as long as ramucirumab is held for 4-6 weeks afterwards. Ramucirumab can be restarted after this time if the patient is asymptomatic, clinically stable and this is considered appropriate by the investigator.). Participants who have unconfirmed disease progression may continue on treatment at the discretion of the Investigator until progression is confirmed by the site provided they have met the conditions detailed in Section 9.2.1.6. Participants who receive confirmatory imaging do not need to undergo the next scheduled tumor imaging if it is less than 4 weeks later; tumor imaging may resume at the subsequent scheduled imaging time point, if clinically stable. Participants who have confirmed disease progression by iRECIST, as assessed by the site, will discontinue study treatment.

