6.4 End of Study

The primary statistical analysis will be performed when 80% of the events for the secondary analysis of PFS have occurred. This will ensure appropriate follow-up time for the primary endpoint of ORR and for the secondary endpoints of PFS and OS.

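### The primary response-rate analysis has two unlinked triggers, and the 6-week minimum at both looks is too short for a confirmed response in the last patient

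*Combined protocol and SAP*

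**What the plan says.** **Final analysis.** Section 3.2: "The primary endpoint analysis will be done after the last accrued patient has been followed for at least 6 weeks". Section 6.4: "The primary statistical analysis will be performed when 80% of the events for the secondary analysis of PFS have occurred", followed by "This will ensure appropriate follow-up time for the primary endpoint of ORR and for the secondary endpoints of PFS and OS". Section 6.4 gives no event number or denominator. Section 9.4 gives no data cut-off.

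**Interim.** Section 4.1 has a "planned interim analysis for futility planned after the initial 13 patients (stage 1) have been followed for at least 6 weeks". The synopsis (Study Design) makes continuation depend on a confirmed response.

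**Scans.** Table 4, footnote 12: "Disease status will be measured by CT scan every 6 weeks (+/- 7 days) for the first 6 months". Section 6.3.5: "The first on-study imaging assessment should be performed at 6 weeks", with a window of 7 days either side of day 42. It adds "Objective response should be confirmed by a repeat imaging assessment" and "Tumor imaging to confirm PR or CR should be performed at least 4 weeks after the first indication of a response is observed".

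**Scoring.** Section 9.4.2 puts every eligible patient with at least one dose in the denominator and counts best response of PR or CR. It does not mention confirmation.

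**Boundaries.** Sections 9.2 and 9.4.1 stop after stage 1 with 1 or fewer responses in 13. The synopsis and section 9.3 stop with none. Section 9.4.1 rejects the treatment with 5 or fewer responses in 34.

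**The concern.** The cut-off for the primary endpoint should be fixed in advance, above all in an open-label single-arm trial with investigator-read response. Here two sections give different triggers, and the text does not say which governs or whether both must be met.

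Neither trigger secures what the endpoint needs. A patient followed for 6 weeks has had at most one scheduled scan. That patient has had none if the first scan falls on days 43–49, which is within the window, yet is in the denominator after one dose. An event count says nothing about any one patient's follow-up.

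At stake is a true responder being scored a non-responder because of the calendar. This matters most at the interim, where a futility stop is hard to undo.

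**Working it through.** **1. The plan's own figures.** Inputs from sections 9.2 and 9.4.1: p0 = 0.10, p1 = 0.25, 13 + 21 patients, stop if ≤1, success if ≥6 of 34.

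- Early stop at 0.10: 0.9^13 + 13(0.1)(0.9^12) = 0.2542 + 0.3672 = 0.621.
- Expected size: 13 + 21(1 − 0.6213) = 20.95.

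Both match section 9.4.1. With P(success) = Σ over x > r1 of Bin(x; 13, p) × P[Bin(21, p) ≥ 6 − x]:

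- stop if ≤1 (r1 = 1): power 0.811, type I error 0.096;
- stop if 0 (r1 = 0): power 0.876, type I error 0.115.

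**2. Scan calendar.**

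| Event | Day |
|---|---|
| First scan (42 ± 7) | 35–49 |
| Earliest confirmation (+28) | 63–77 |
| Second scheduled scan (84 ± 7) | 77–91 |
| Stated minimum follow-up | 42 |

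The minimum is 21 days short of the earliest possible confirmation. A response first seen at week 12–13 needs week 16–17 or later.

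**3. How many patients are affected.** Section 3.2 plans 1 patient per 2 months, or 8.7 weeks. When the newest patient has 6 weeks, the one before has 6 + 8.7 = 14.7 weeks, enough to confirm a first-scan response. So about one patient per look is affected.

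**4. Effect of one uncountable patient.** This takes a look at exactly 6 weeks, confirmation required, and every response first seen at week 6. For the final look, replace Bin(21) by Bin(20). For the interim, decide on 12 patients and count patient 13 again at the end.

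| | Stop if ≤1 | Stop if 0 |
|---|---|---|
| Power, no loss | 0.811 | 0.876 |
| Loss at final only | 0.798 | 0.859 |
| Loss at interim only | 0.785 | 0.871 |
| Loss at both | 0.774 | 0.854 |
| Early stop at 0.25, no loss → interim loss | 0.127 → 0.158 | 0.024 → 0.032 |
| Type I error, no loss → both | 0.096 → 0.082 | 0.115 → 0.102 |

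For example, early stop under stop if ≤1 goes from 0.0238 + 0.1029 = 0.127 with 13 patients to 0.0317 + 0.1267 = 0.158 with 12.

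**5. Later responses.** Assume 25% (or 50%) of responses first appear at the week-12 scan. The documents give no such share. A response counts once follow-up reaches 10 weeks (seen at week 6) or 16 weeks (seen at week 12).

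| Power at 0.25 | Stop if ≤1 | Stop if 0 |
|---|---|---|
| 6-week minimum, both looks | 0.763 (0.752) | 0.848 (0.841) |
| 12–13-week cut-off alone | 0.801 (0.792) | 0.870 (0.865) |
| 12–13 weeks, unconfirmed responses followed | 0.811 | 0.876 |

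**6. The event trigger.** If the denominator is all 34 (assumed), 80% is 27.2, so 28 events, and 6 patients, including the last, can be event-free with any follow-up. Simulation: 34 patients 2 months apart, exponential PFS, no censoring.

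| Median PFS (months) | 28th event before last patient enrolled | Before last enrolled + 6 weeks |
|---|---|---|
| 3 (assumed) | >99% | >99% |
| 6 (assumed) | 87% | 94% |
| 9.7 (phase 1 NSCLC cohort, section 1.5.2) | 31% | 46% |
| 12 (assumed) | 11% | 19% |

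**7. Accrual.** 34 patients at 1 per 2 months take 33 × 2 = 66 to 34 × 2 = 68 months. Section 3.2 says 60. This is a planning figure with no effect on inference.

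**The case against.** **The triggers are compatible.** Section 3.2 sets a floor and section 6.4 an event count, so one analysis can meet both, and nothing says a look will be taken on day 42. This is a fair reading, but the text does not state it. Even if both must be met, only 6 weeks is guaranteed for the last patient.

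**Confirmation is not settled.** Section 9.4.2 and Appendix 1 define best response without it, and section 6.3.5 concerns imaging. If unconfirmed responses count, the newest patient is lost only when the first scan falls after day 42. With an assumed 50% chance of that at each look, power is 0.792 (stop if ≤1) or 0.865 (stop if 0). This reduces the size of the problem, and it shows that the endpoint definition needs settling too.

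**Power below 80% needs one particular boundary.** The interim rule that names confirmed responses is the synopsis rule, which stops only at 0, and there power stays at 0.84 or above. This stands. The conflict between the two boundaries is a separate matter.

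**A sensible team would wait** for a pending confirmation before stopping. Probably so, but the plan does not require it.

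**The error is small and conservative.** That is correct at the planned accrual. Section 3.1.4 considers more sites for stage 2. If faster accrual left 2 or 3 patients uncountable at the final look (assumed), power under stop if ≤1 would be 0.784 or 0.767.

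**Conclusion.** The concern holds and should be fixed. Sections 3.2 and 6.4 leave the primary cut-off open between two triggers. The 6-week minimum falls before any response can be confirmed on scheduled scans, and the assurance in section 6.4 about response-rate follow-up is not correct as written.

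The effect is modest: about one patient per look and, with both looks at the minimum, a loss of 3.7 points of power (0.811 to 0.774) under stop if ≤1 or 2.2 points (0.876 to 0.854) under stop if 0. Type I error falls as well. These figures assume the planned accrual rate, confirmation required and all responses first seen at week 6. The calendar finding needs none of these except confirmation. The accrual-duration mismatch carries no weight here.

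**What to change.** 1. In sections 3.2 and 6.4, state one response-rate cut-off: every treated patient has had the first scheduled scan and time for a confirmatory scan at least 4 weeks later (about 12–13 weeks, the second scheduled scan with its window), or has progressed, died or withdrawn. Any response still unconfirmed then is followed to its confirmatory scan before it is scored.
2. Use the same rule for the 13-patient look in section 4.1. A decision to continue can be made as soon as enough confirmed responses are in. Only a stop has to wait.
3. State in section 9.4.2 whether the response rate counts confirmed responses, in line with the synopsis and section 6.3.5.
4. Remove the section 6.4 claim that 80% of PFS events secures response-rate follow-up. Time PFS and OS by a stated event number or calendar date, not before the response-rate cut-off.
5. In section 3.2, restate enrolment as 66–68 months, or the rate as about 1 patient per 1.8 months (60/34 = 1.76; 60/33 = 1.82).

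**Cost.** Protocol wording. Each look moves about 6–7 weeks beyond the stated minimum, or up to about 11 weeks if a response first seen at the second scan awaits confirmation. The planned total of 34 does not change, and no scans are added beyond those in section 6.3.5. The plan does not say whether accrual pauses at the interim. If it does not, one or two more patients could enter before a futility stop (11/8.7 = 1.3), so this should be stated as well.
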